### 8.1 METHOD OF ASSESSMENT

---

In addition to clinical examination, radiographic evaluation will be used in all subjects enrolled. CT scan is the preferred method for radiographic tumor assessment. MRI scanning may be used at the investigator's discretion in subjects for whom this may be a preferred alternative to CT scanning; however, if MRI is performed, a non-contrast CT of the chest should be performed. Contrast-enhanced scanning is preferred, but iodine-containing or gadolinium contrast material may be omitted in subjects for whom use of a contrast agent would be medically contraindicated. Chest x-ray, ultrasound, endoscopy, laparoscopy, PET, radionuclide scans, or tumor markers will not be considered for response assessment.

For radiographic evaluations, the same method of assessment and the same technique (e.g., scan type, subject position, dose of contrast, injection/scan interval) should be used to characterize each identified and reported lesion at baseline and during study treatment and follow-up. However, if a subject is imaged without contrast at baseline, subsequent assessments should be performed with contrast, unless medically contraindicated.

Relevant clinical and radiographic information required to make each tumor status assessment must be requested for source verification.

### 8.2 IDENTIFICATION AND MEASUREMENT OF TUMOR LESIONS AND ORGANOMEGALY

---

#### 8.2.1 TARGET LESIONS

---

At baseline, up to 6 lymph nodes should be selected as target lesions that will be used to quantitate the status of the disease during study treatment. Ideally, the target lesions should be located in disparate regions of the body. Only peripheral nodes need be selected as target lesions. However, it

is optimal if mediastinal and retroperitoneal areas of disease are assessed whenever these sites are involved.

Target lesions will be measured and recorded at baseline and as per the study assessment schedule. The cross-sectional dimensions (the largest cross-sectional diameter, i.e., the LD × LPD) will be recorded (in cm) for each target lesion. The product of the perpendicular diameters (PPD) (in cm^2) for each target lesion and the sum of the products (SPD) (in cm^2) for all target lesions will be calculated and recorded. The baseline SPD will be used as references by which objective tumor response will be characterized during treatment. The nadir LD of individual lesions and the nadir SPD will be used as references by which CLL progression will be characterized. All LD and LPD diameters will be reported in centimeters and all PPDs and SPDs will be reported in centimeters squared.

A nodal mass may be selected as a nodal target lesion if it is both abnormal and measurable at baseline. A lymph node lesion is considered abnormal if it has a single diameter that is > 1.5 cm and is considered measurable if it has 2 perpendicular diameters that can be accurately measured in cross section with the LD being ≥ 1.0 cm and the LPD also being ≥ 1.0 cm.

A new node that measures >1.5 cm in the LD and >1.0 cm in the LPD will be considered progressive disease.

In cases in which a large lymph node mass has split into multiple components, all subcomponents regardless of size will be used in calculating the SPD. Progression of the lesion will be based on the SPD of sub-components. Lesion sub-components will have the true PPDs calculated. Similarly, lesion sub-components that are visible but neither abnormal nor measurable will have the default PPD of 1.0 cm^2 (1.0 cm × 1.0 cm) used in calculating the SPD.

If lesions merge, a boundary between the lesions will be established so the LD of each individual lesion can continue to be measured. If the lesions have merged in a way that they can no longer be separated by this boundary, the newly merged lesion will be measured bi-dimensionally.

---

## 8.2.2 SPLEEN AND LIVER

---

Both the spleen and liver will be assessed by CT/MRI scan and/or by physical examination at baseline and as per the study assessment schedule. The baseline and nadir values for the longest vertical dimension (LVD) of each organ will be used as reference to further characterize the objective tumor response of the measurable dimensions of the CLL during treatment. All spleen and liver LVD measurements should be recorded in centimeters.

By imaging, the spleen will be considered enlarged if it is >12 cm in LVD, with the LVD being obtained by multiplying the number of sections on which the spleen is visualized by the thickness of the sections (e.g., if the spleen is seen in 14 contiguous cross-sectional images with 0.5-cm thickness, the LVD is recorded as 7 cm).

For subjects with splenomegaly at baseline or at the splenic LVD nadir, respective response and progression evaluations of the spleen will consider only changes relative to the enlargement of the spleen at baseline or nadir, not changes relative to the total splenic LVD.

A 50% decrease (minimum 2 cm decrease) from baseline in the enlargement of the spleen in its LVD or decrease to  $\leq 12$  cm by imaging is required for declaration of a splenomegaly response. Conversely, an increase in splenic enlargement by  $\geq 50\%$  from nadir (minimum increase of 2 cm) is required for declaration of splenic progression. By imaging, the liver will be considered enlarged if it is  $>18$  cm in LVD.

A 50% decrease (minimum 2 cm decrease) from baseline in the enlargement of the liver in its LVD or decrease to  $\leq 18$  cm is required for declaration of a hepatomegaly response. Conversely, an increase in liver enlargement by  $\geq 50\%$  from nadir (minimum increase of 2 cm) is required for declaration of hepatic progression.

---

### 8.2.3 NON-TARGET LESIONS

---

Any other measurable and abnormal nodal lesions not selected for quantitation as target lesions may be considered non-target lesions. In addition, non-measurable evidence of CLL such as nodal lesions with both diameters  $<1.0$  cm, extra-nodal lesions, bone lesions, leptomenigeal disease, ascites, pleural or pericardial effusions, lymphangitis of the skin or lung, abdominal masses that are not confirmed and followed by imaging techniques, cystic lesions, previously irradiated lesions, and lesions with artifacts may be considered as non-target disease.

The presence or absence of non-target disease should be recorded at baseline and as per the study assessment schedule. If present at baseline, up to 6 non-target lesions should be recorded. The non-target disease at baseline will be used as a general reference to further characterize regression or progression of CLL during assessments of the objective tumor response during treatment. Measurements are not required and these lesions should be followed as “present” or “absent”.

---

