## 8.4 COMPLETE RESPONSE

---

To satisfy criteria for a CR, all of the following criteria must be met:

- No evidence of new disease
- ALC in peripheral blood of  $<4 \times 10^9/L$
- Regression of all target nodal masses to normal size  $\leq 1.5$  cm in the LD
- Normal spleen and liver size
- Regression to normal of all nodal non-target disease and disappearance of all detectable non-nodal, non-target disease

- Morphologically negative bone marrow defined as <30% of nucleated cells being lymphoid cells and no lymphoid nodules in a bone marrow sample that is normocellular for age
- Peripheral blood counts meeting all of the following criteria:
  - ANC  $>1.5 \times 10^9/L$  without need for exogenous growth factors (e.g., G-CSF)
  - Platelet count  $\geq 100 \times 10^9/L$  without need for exogenous growth factors
  - Hemoglobin  $\geq 110 \text{ g/L}$  (11.0 g/dL) without red blood cell transfusions or need for exogenous growth factors (e.g., erythropoietin)

Subjects who fulfill all the criteria for a CR (including bone marrow criteria) but who have a persistent anemia, thrombocytopenia, or neutropenia or a hypocellular bone marrow that is related to prior or ongoing drug toxicity (and not to CLL) will be considered as a CR with incomplete marrow recovery (CRi).

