## 8.7 DEFINITIVE DISEASE PROGRESSION

---

The occurrence of any of the following events indicates definitive PD:

- Evidence of any new disease:
  - A new node that measures >1.5 cm in the LD and >1.0 cm in the LPD
  - New or recurrent splenomegaly, with a minimum LVD of 14 cm
  - New or recurrent hepatomegaly, with a minimum LVD of 20 cm
  - Unequivocal reappearance of an extra-nodal lesion that had resolved
  - A new unequivocal extra-nodal lesion of any size
  - \*New non-target disease (e.g., effusions, ascites, or other organ abnormalities related to CLL).

\*Isolated new effusions, ascites, or other organ abnormalities are not sufficient evidence alone of PD unless histologically confirmed. Thus, a declaration of PD should not be made if this is the only manifestation of apparently new disease.

- Evidence of worsening of target lesions, spleen or liver, or non-target disease:
  - Increase from the nadir by  $\geq 50\%$  from the nadir in the SPD of target lesions
  - Increase from the nadir by  $\geq 50\%$  in the LD of an individual node or extra-nodal mass that now has an LD of >1.5 cm and an LPD of > 1.0 cm
  - Splenic progression, defined as an increase in splenic enlargement by  $\geq 50\%$  from nadir (with a minimum 2 cm increase and a minimum LVD of 14 cm)
  - Hepatic progression, defined as an increase in hepatic enlargement by  $\geq 50\%$  from nadir (with a minimum 2 cm increase and minimum LVD of 20 cm)
  - Unequivocal increase in the size of non-target disease (e.g., effusions, ascites, or other organ abnormalities related to CLL)
  - Transformation to a more aggressive histology (e.g., Richter's syndrome) as established by biopsy (with the date of the biopsy being considered the date of CLL progression if the subject has no earlier objective documentation of CLL progression).
- Decrease in platelet count or hemoglobin that is attributable to CLL, is not attributable to an autoimmune phenomenon, and is confirmed by bone marrow biopsy showing an infiltrate of clonal CLL cells
  - The current platelet count is  $< 100 \times 10^9/L$  and there has been a decrease by  $> 50\%$  from the highest on-study platelet count
  - The current hemoglobin is  $< 110 \text{ g/L}$  (11.0 g/dL) and there has been a decrease by  $> 20 \text{ g/L}$  (2 g/dL) from the highest on-study hemoglobin

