## 8.8 NON-EVALUABLE

---

In a subject who does not have evidence of PD, the occurrence of any of the following conditions indicates a response status of NE:

- There are no images or inadequate or missing images

- Images of the liver and spleen are missing at that time point (with the exception that absence of splenic images will not result in an NE designation in a subject known to have undergone splenectomy).

A time-point will be considered to have a response of NE if any target lesion is missing. PD may be assigned at any time point regardless of the extent of missing target or non-target lesions. Missing non-target lesions will not impact the ability to assess for response or disease progression.

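### The 50% diameter rule for progression covers lesions that need not be measured, and the rule on missing non-target lesions conflicts with the complete-response criteria

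*Combined protocol and SAP*

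**What the plan says.** Section 8.2.1 takes up to six lymph nodes as target lesions and requires two diameters for each at baseline and at scheduled assessments. It adds: "Only peripheral nodes need be selected as target lesions". It does call it optimal to assess mediastinal and retroperitoneal disease where those areas are involved.

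Section 8.2.3 allows everything else to be non-target. For nodes: "Any other measurable and abnormal nodal lesions not selected for quantitation as target lesions may be considered non-target lesions". The list of non-measurable evidence includes "extra-nodal lesions, bone lesions, leptomenigeal disease, ascites, pleural or pericardial effusions". Up to six non-target lesions are recorded if present at baseline. On follow-up: "Measurements are not required and these lesions should be followed as" present or absent.

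The response rules then ask for the following.

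- **Progression (Section 8.7).** One limb is an increase of at least 50% from nadir "in the LD of an individual node or extra-nodal mass that now has an LD of >1.5 cm", with a perpendicular diameter above 1.0 cm. A separate limb is "Unequivocal increase in the size of non-target disease", which has no numeric threshold.
- **Complete response (Section 8.4).** "Regression to normal of all nodal non-target disease and disappearance of all detectable non-nodal, non-target disease".
- **Partial response (Section 8.5).** No non-target worsening that amounts to definitive progression.
- **Missing data (Section 8.8).** "Missing non-target lesions will not impact the ability to assess for response or disease progression". A missing target lesion, by contrast, makes the time point non-evaluable (NE).

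Appendix A applies a 50% diameter rule to any previous site of disease. The treating investigator determines response and progression (Section 8), and Table 2 in Section 5 states that there is no central radiology review.

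**The concern.** An endpoint event is defined by a quantity that sites are told they need not collect. An extra-nodal mass cannot be a target lesion, so nothing requires its diameter at any visit. The same holds for a node left out of the target set. Without a recorded nadir, a 50% increase from nadir has no reference value.

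The CR criteria raise two further difficulties. For nodes the test is a return to normal size, which a two-level code does not express. And if missing non-target lesions have no effect on response assessment, a CR can be entered although part of what Section 8.4 requires was never looked at.

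PFS and DOR are at stake, and the synopsis makes them the primary objectives for former Arm A subjects (secondary for Arms B, C and D). So is the CR rate, which Section 9.8.1 analyses in the same way as ORR.

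**Working it through.** No sample size, power or error-rate figure bears on this point, and the plan states no figure to reproduce. The check sets the rules side by side and adds short arithmetic. Lesion sizes below are assumed for illustration; thresholds and scan intervals are the protocol's.

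1. **The 50% diameter limb.** Inputs: Section 8.7 needs the current LD, the nadir LD and the current LPD. Section 8.2.1 requires these for target nodes only; Section 8.2.3 requires none for other lesions. Take an extra-nodal mass with a nadir of 2.0 × 1.5 cm that now measures 3.0 × 2.0 cm. Change in LD = (3.0 − 2.0) / 2.0 = 50%; LD 3.0 cm exceeds 1.5 cm; LPD 2.0 cm exceeds 1.0 cm. All parts of the limb are met. The required record reads present, then present. Neither the nadir nor the increase can be recovered from it.

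2. **Non-target nodes and CR.** Take a non-target node that shrinks from 2.4 cm to 1.2 cm. Section 8.4 sets no separate limit for non-target nodes; using its 1.5 cm limit for target nodes, 1.2 cm is normal and this CR criterion is met. If the node is visible, it may still be coded present, as would a node that stayed at 2.4 cm. For non-nodal disease the CR test is disappearance, which present/absent captures, so this difficulty is confined to nodes.

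3. **Missing non-target disease and CR.** Suppose a baseline pleural effusion is not assessed at a visit where every target node is at or below 1.5 cm and the other CR criteria are met. Section 8.8 lets the response assessment go ahead unaffected. Section 8.4 requires the effusion to have disappeared, and nothing shows that it has. The cap of six recorded non-target lesions adds to this, because Section 8.4 refers to all such disease.

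4. **Possible delay from one uncalled progression.** Scans fall at about cycles 3, 6 and 12, then at least every 12 cycles unless clinically indicated sooner. With 28-day cycles:
   - cycle 6 to cycle 12: 6 × 28 = 168 days;
   - after cycle 12: up to 12 × 28 = 336 days.

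   These are the gaps to the next scheduled scan if growth is not called at one scan. They are not expected shifts in PFS or DOR.

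5. **Which estimates move.** ORR = CR + PR. Moving one subject from CR to PR changes the sum by −1 + 1 = 0, so only the CR and PR rates move. A missed progression acts mainly on PFS and DOR. It reaches ORR only if it lets a PR stand that Section 8.5 would have ruled out.

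**The case against.** Much of the case on the other side is sound. Section 8.2.3 does not forbid measurement. The investigator decides from CT or MRI rather than from an eCRF code, and Section 8.1 calls for the information behind each tumour assessment to be requested for source verification. The unequivocal-increase limb needs no recorded diameter and can be called from serial images. New and reappearing extra-nodal lesions are progression events in their own right, progression may be assigned despite missing lesions, and absent or inadequate images already make a time point NE. The Section 8.8 sentence can be read as saying only that a missing non-target lesion does not trigger NE, leaving the CR criteria in force.

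A reader might therefore infer more than the text supports: that growth outside the target nodes is lost, so PFS and DOR are overstated, and that CRs are wrongly counted. The documents do not show this. A large deep mass that doubles in size can be called as an unequivocal increase whatever its code. Nothing says that a present code overrides the CR criteria for a node that has become normal. Any percentage of affected CRs would be a guess.

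Two points survive. The diameter limb has no required data behind it, so two investigators can reach different answers and a monitor cannot check either from the record. And Section 8.8 says in terms that response assessment is unaffected. The narrower reading is possible but not written down, so an unsupported CR remains open.

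**Conclusion.** The concern holds as two internal conflicts. Section 8.7 sets a numeric progression rule for individual nodes and extra-nodal masses, while Sections 8.2.1 and 8.2.3 require diameters for target nodes only. Section 8.8 discounts missing non-target lesions, while Section 8.4 makes CR depend on all of them.

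The consequence is a risk, not a demonstrated error: progression in non-target disease may be missed, late or unverifiable, and CR may be misclassified in either direction. The size cannot be computed, because the documents give no rate of progression confined to non-target disease and no rate of unassessed non-target lesions. The longest scheduled gap behind one uncalled progression is 336 days after cycle 12, assuming on-treatment scans at the minimum frequency. ORR is little exposed. The study tests no hypothesis, so what suffers is the reliability of descriptive PFS, DOR and CR estimates. This justifies a correction given how little it costs.

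**What to change.** 1. **Section 8.2.3 and the eCRF.** Replace present/absent with five codes: absent; normal (node LD 1.5 cm or less); present, not increased; unequivocally increased; not assessed. Record LD and LPD of measurable extra-nodal masses and measurable non-target nodes at baseline and at every scan already scheduled. Recording them only when progression is called would leave no nadir for the 50% rule.

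2. **Section 8.8.** State that a missing non-target lesion does not by itself make the time point NE and that progression stays assignable, but that CR or CRi cannot be assigned where any baseline non-target disease was not assessed. The best category at that time point is PR, if the other PR criteria are met. PR also requires no non-target worsening, so the not-assessed code should remain visible in the listings.

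3. **Reconcile** Sections 8.2.3, 8.4, 8.7 and 8.8 with Appendix A, including its diameter rule for any previous site and the cap of six recorded lesions against the CR requirement covering all non-target disease.

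The cost is a code-list change, a few sentences and modest extra data entry, with no new scans or readers. The CR rate may come out slightly lower.

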## 8.3 DEFINITIONS OF TUMOR RESPONSE AND PROGRESSION

---

Responses will be categorized as CR, PR, SD, or PD. In addition, a response category of not evaluable (NE) is provided for situations in which there is inadequate information to otherwise categorize response status.

The best overall response will be determined. The best overall response is the best response recorded from the start of treatment until disease/recurrence progression (taking as a reference for disease progression the smallest measurements recorded since treatment started). Where imaging data are available, these data will supersede physical examination data in determining tumor status.

---

## 8.4 COMPLETE RESPONSE

---

To satisfy criteria for a CR, all of the following criteria must be met:

- No evidence of new disease
- ALC in peripheral blood of  $<4 \times 10^9/L$
- Regression of all target nodal masses to normal size  $\leq 1.5$  cm in the LD
- Normal spleen and liver size
- Regression to normal of all nodal non-target disease and disappearance of all detectable non-nodal, non-target disease

- Morphologically negative bone marrow defined as <30% of nucleated cells being lymphoid cells and no lymphoid nodules in a bone marrow sample that is normocellular for age
- Peripheral blood counts meeting all of the following criteria:
  - ANC  $>1.5 \times 10^9/L$  without need for exogenous growth factors (e.g., G-CSF)
  - Platelet count  $\geq 100 \times 10^9/L$  without need for exogenous growth factors
  - Hemoglobin  $\geq 110 \text{ g/L}$  (11.0 g/dL) without red blood cell transfusions or need for exogenous growth factors (e.g., erythropoietin)

Subjects who fulfill all the criteria for a CR (including bone marrow criteria) but who have a persistent anemia, thrombocytopenia, or neutropenia or a hypocellular bone marrow that is related to prior or ongoing drug toxicity (and not to CLL) will be considered as a CR with incomplete marrow recovery (CRi).

## 8.5 PARTIAL RESPONSE

---

To satisfy criteria for a PR, all of the following criteria must be met:

- No evidence of new disease
- A change in disease status meeting  $\geq 2$  of the following criteria, with 2 exceptions in which only 1 criterion is needed: 1) only lymphadenopathy is present at baseline; 2) only lymphadenopathy and lymphocytosis are present at baseline. In these 2 cases, only lymphadenopathy must improve to the extent specified below:
  - In a subject with baseline lymphocytosis ( $ALC \geq 4 \times 10^9/L$ ), a decrease in peripheral blood ALC by  $\geq 50\%$  from baseline or a decrease to  $<4 \times 10^9/L$
  - A decrease by  $\geq 50\%$  from the baseline in the SPD of the target nodal lesions
  - In a subject with enlargement of the spleen at baseline, a splenomegaly response as defined in [Section 8.2.2](#)
  - In a subject with enlargement of the liver at baseline, a hepatomegaly response as defined in [Section 8.2.2](#)
  - A decrease by  $\geq 50\%$  from baseline in the CLL marrow infiltrate or in B-lymphoid nodules
- No target, splenic, liver, or non-target disease with worsening that meets the criteria for definitive PD
- Peripheral blood counts meeting 1 of the following criteria:
  - ANC  $>1.5 \times 10^9/L$  or  $>50\%$  increase over baseline without need for exogenous growth factors (e.g., G-CSF)
  - Platelet count  $\geq 100 \times 10^9/L$  or  $\geq 50\%$  increase over baseline without need for exogenous growth factors
  - Hemoglobin  $\geq 110 \text{ g/L}$  (11.0 g/dL) or  $\geq 50\%$  increase over baseline without red blood cell transfusions or need for exogenous growth factors (e.g., erythropoietin)

